#### 6. RECRUITMENT METHODS

- *Describe the source of potential subjects*
- Describe the methods that will be used to identify potential subjects
- Describe any materials that will be used to recruit subjects. A copy of any advertisements (flyers, radio scripts, etc.) should be submitted along with the protocol.
- If monetary compensation is to be offered, this should be indicated in the protocol

We are aiming to recruit 30 patients from the Northwell fertility clinic at the point of care for their infertility work-up. The clinicians in this study will see the potential subjects in their routine clinical care.

The physicians in the Department of Radiology and Northwell Health Fertility will play the dual role of clinician and research investigator.

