#### Secondary Endpoint:

- Quantification of level of patient pain in regard to sonoHSG versus HSG

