#### 11. RESEARCH PROCEDURES

- *Include a detailed description of all procedures to be performed on the research subject and the schedule for each procedure.*
- *Include any screening procedures for eligibility and/or baseline diagnostic tests*

- Include procedures being performed to monitor subjects for safety or minimize risks
- *Include information about drug washout periods*
- If drugs or biologics are being administered provide information on dosing and route of administration
- Clearly indicate which procedures are only being conducted for research purposes.
- If any specimens will be used for this research, explain whether they are being collected specifically for research purposes.
- Describe any source records that will be used to collect data about subjects
- Indicate the data to be collected, including long term follow-up

Patients will be presented with the study information at the point of contact at the fertility clinic. They will then be contacted via phone prior to their scheduled appointment. A detailed overview of the study will be presented as well as the consent form. Upon verbal agreement over the phone, the clinician and/or study coordinator will go over the consent process in person on the day of the scheduled visit. As part of this study, subjects will have both the HSG and SonoHSG performed consecutively. The HSG will be performed as part of standard of care and the sonoHSG will be performed as part of research. In order to reduce bias, the procedures will be randomized in REDCap before each subject's scheduled visit. The clinicians will be blinded to the results of each procedure until both procedures have been completed.

The pain scale will be administered verbally immediately after each procedure by the technician/other study personnel in the procedure room.

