#### Randomization Scheme

The randomization tables will be set up by the biostatistics department and the randomization model will be set up by a REDCap administrator. The study coordinator will run the randomization in REDCap after the subject has signed their consent form and prior to the initiation of the study procedures. The coordinator will then communicate to the study PI and Co-Investigators the randomization assignment.

Following is the schedule of events that will be followed for each potential subjects:

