#### Schedule of Events:

	Pre-Visit	Visit 1	Follow-Up Visit (1-3 weeks)
Recruit Subject	X	X	
Evaluate Eligibility	X	X	
Initiate Informed Consent	X	X	
Obtain Written Informed Consent		X	
Collect Demographic Information		X	

HSG and sonoHSG (order decided via randomization)	X	
Administer the Pain Scale Survey (following each procedure)	X	
Follow-up with subject via phone to assess any complications/infections		Х

The procedures that would account as being research are obtaining informed consent, administering the pain scale surveys, performing the sonoHSG and the follow-up phone call.

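### Pain is asked aloud in the procedure room by staff who will know which procedure was done, and only after each of two consecutive procedures: open to an interviewer shift and to unequal residual pain that the order terms cannot remove

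*Protocol*

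**What the plan says.** The only secondary endpoint in Protocol section 10 is "Quantification of level of patient pain in regard to sonoHSG versus HSG". Section 11 states that "subjects will have both the HSG and SonoHSG performed consecutively", and the Schedule of Events places both at Visit 1 in randomised order, with the pain survey following each one. No pain score is scheduled before either procedure.

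On who asks, how and when, section 11 says: "The pain scale will be administered verbally immediately after each procedure by the technician/other study personnel in the procedure room". The only masking is of test results: "The clinicians will be blinded to the results of each procedure until both procedures have been completed". Under the Randomization Scheme, "The coordinator will then communicate to the study PI and Co-Investigators the randomization assignment". Nothing masks the person asking about pain to the procedure.

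Section 12 analyses pain by repeated measures ANOVA with treatment, order and their interaction, dropping the interaction if it is not significant. Sections 3 and 19 already describe sonoHSG as the less painful examination.

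**The concern.** Two separate mechanisms could move the pain comparison.

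- **Interviewer shift.** A spoken answer given to someone who has just watched the procedure, in a programme that expects one procedure to hurt less, can lean toward the expected answer. A lean tied to the procedure looks exactly like a treatment effect.
- **Unequal residual pain.** The second score is taken with no record of the pain already present. Section 3 attributes painful cervical manipulation and sometimes strong uterine contractions to HSG, so on the protocol's own account HSG may leave more behind than sonoHSG. That would pull the estimate toward no difference.

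Pain is one of the two measures of success in section 2, patient comfort is a stated goal in section 4, and section 8 foresees a larger trial. The two mechanisms run in opposite directions, so a reported difference could be too large or too small. A score that was never collected cannot be recovered by any later analysis plan.

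**Working it through.** The protocol gives no pain SD, correlation, expected difference or residual, so there is no stated figure to reproduce.

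**Inputs from the protocol:** 30 women (up to 50), randomised order, one score after each procedure, and the model terms in section 12.

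**Assumed:** 15 women per order; a 0–10 scale; SD of a single score 2 (range 2 to 2.5); within-woman correlation 0.5 (range 0.3 to 0.5); true HSG-minus-sonoHSG difference D = 2 points; residual pain 0 to 2 points; two-sided 5% tests; order coded as sequence.

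**1. Effect of residual pain.** Let cH and cS be the residual pain that HSG and sonoHSG leave in the following score.
- HSG first: expected difference = D − cH.
- SonoHSG first: expected difference = D + cS.
- Average of the two orders = D − (cH − cS)/2.

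With D = 2:
- cH = 1, cS = 1: 2.00 (no bias)
- cH = 1, cS = 0: 1.50
- cH = 2, cS = 1: 1.50
- cH = 2, cS = 0: 1.00

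Simulation with 20,000 trials per setting agrees to within 0.01. With balanced orders the result is the same whether or not the interaction is kept. If each procedure leaves a fraction f of its own pain, then cH − cS = f × D and the attenuation is f/2: 5%, 12.5% and 25% for f = 10%, 25% and 50%.

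**2. Unequal numbers per order.** With an 18/12 split and an equal residual of 1 point, the estimate stays at 2.00 if the interaction is kept. If it is dropped and women are pooled, the estimate is 2 − (18 × 1 − 12 × 1)/30 = 1.80.

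**3. Can the planned model detect unequal residual pain?** With order as sequence, the treatment-by-order interaction tests the period effect, including the average residual. The order main effect tests cH − cS. It compares each woman's mean score between orders:
- Expected gap = (cH − cS)/2, that is 0.5 for a 1-point and 1.0 for a 2-point excess.
- Variance of a woman's mean = SD² × (1 + correlation)/2 = 4 × 1.5/2 = 3.
- Standard error = √(3 × 2/15) = 0.63.
- Gap divided by standard error = 0.79 and 1.58.

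Simulated power with 30 women is 12% and 33% (about 10–14% and 23–38% over the assumed ranges). With 50 women it is 17% and 52% (about 13–19% and 36–57%). A significant order effect flags the problem but leaves the treatment estimate biased.

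**4. Interviewer shift.** If the way of asking widens the HSG-minus-sonoHSG gap by b points in either order, the estimate becomes D + b − (cH − cS)/2. With b = 0.5 and equal residuals it is 2.50. Randomised order does not reduce it.

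**5. Scale against precision.** The 95% half-width for 30 women is 2.045 × SD of the within-woman difference/√30. For difference SDs of 2, 2.5 and 3 it is 0.75, 0.93 and 1.12 points. A shift of 0.5 to 1 point would be of the same order, but nothing in the protocol says how large a shift to expect.

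**6. Cost of using first procedures only.** The standard error is 2 × √(2/15) = 0.73, against 2/√30 = 0.37 for the within-woman comparison (difference SD = 2 × √(2 × 0.5) = 2). It is free of carry-over but has half the precision, so it suits a sensitivity analysis.

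**The case against.** The plan has real safeguards. Order is randomised, expressly to reduce bias, and the pain model carries order and its interaction with treatment. A reader might infer that any pain left from the first procedure contaminates the comparison. It does not: residual pain common to both orders cancels when the orders are balanced or the interaction is retained. Nor is unequal residual pain undetectable, because the order main effect can test it, though weakly. The first-procedure scores will exist anyway, and an analysis confined to them may already be planned in a SAP that was not at hand.

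A reader might also infer a personal stake from section 6, where physicians "will play the dual role of clinician and research investigator". That sentence concerns physicians, whereas section 11 gives the question to a technician or other study staff, so it does not show that the person asking has such a stake. The survey form is not shown and may already carry a fixed wording that is read aloud. That the asker knows the procedure is an inference, though a safe one for someone in the room.

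Finally, this is a secondary endpoint in a pilot sized on feasibility. The primary concordance criterion is unaffected, and every size above is assumed.

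All of this stands. It narrows the point without removing it: neither randomised order nor the model touches a shift tied to the procedure, and half of any excess residual pain remains in the estimate.

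**Conclusion.** The point holds as a risk, not as a demonstrated bias. The pain comparison is open to an interviewer shift, which would enter the estimate in full, and to unequal residual pain, which would attenuate it by half the excess. For a true difference of 2 points, a 1-point excess after HSG gives 1.5 and a 2-point excess gives 1.0, with about 12% and 33% power to notice at 30 women. These figures assume SD 2, correlation 0.5 and 15 women per order; the protocol supplies none of them. No net direction can be claimed. The matter is minor for the trial as a whole, but the repair is cheap and can only be made before data collection.

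**What to change.** In section 11 and the Schedule of Events:

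- Replace the spoken question with the same pain scale marked by the patient herself, on a card or REDCap page, under one fixed written instruction, immediately after each procedure and before any discussion with the operator.
- Add the same score immediately before each procedure.

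In section 12:

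- Keep the planned analysis of the post-procedure scores as the main one.
- Report two sensitivity analyses: the change from the pre-procedure score, and the comparison of first procedures only.

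The cost is a printed card or a REDCap page, two extra short scores per woman and slightly more handling in the room. No extra staff are needed, and the procedures and their timing are unchanged. Two limits remain: the patient still knows which procedure she had, so her own expectation is not removed, and change scores may be noisier than the post-procedure scores.

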#### Randomization Scheme

The randomization tables will be set up by the biostatistics department and the randomization model will be set up by a REDCap administrator. The study coordinator will run the randomization in REDCap after the subject has signed their consent form and prior to the initiation of the study procedures. The coordinator will then communicate to the study PI and Co-Investigators the randomization assignment.

Following is the schedule of events that will be followed for each potential subjects:

#### Schedule of Events:

	Pre-Visit	Visit 1	Follow-Up Visit (1-3 weeks)
Recruit Subject	X	X	
Evaluate Eligibility	X	X	
Initiate Informed Consent	X	X	
Obtain Written Informed Consent		X	
Collect Demographic Information		X	

HSG and sonoHSG (order decided via randomization)	X	
Administer the Pain Scale Survey (following each procedure)	X	
Follow-up with subject via phone to assess any complications/infections		Х

The procedures that would account as being research are obtaining informed consent, administering the pain scale surveys, performing the sonoHSG and the follow-up phone call.

#### Data to be collected and when the data is to be collected

#### Collection of personal data to avoid duplicating records

The patient's name, medical record number, age, and health and medical information on diagnoses and medications will be recorded on the Study Eligibility Form to determine eligibility and avoid duplicating records. If the patient meets study eligibility criteria, the patient will be presented with the opportunity of participation in the study. If the patient consents to participate in the study, the subject's name, medical record number, and assigned Subject ID will be recorded on the Coded Identifier List. The hardcopy Study Eligibility Forms and Coded Identifier List will be stored in a locked file cabinet in the Principal Investigator's (PI) office with access restricted to the PI and study staff designated by the PI.

#### Subject ID

A unique Subject ID will be assigned for each enrolled subject and this identifier will follow the subject throughout the course of the study.

#### Data to be collected/obtained

The Data Collection Form will be completed for each enrolled patient. The data collection form contains the following categories of information to be collected/obtained for each subject:

- Patient record demographic data
- Patient record data on pre-existing co-morbid conditions or underlying disease
- Results of HSG and SonoHSG
- Response to evaluation survey with pain scale

The information that links the subject ID with the PHI (the Coded Identifier List) will be kept in the PI's locked office and separate from the Data Collection Forms. Coded data from the Data Collection Form will be collected and stored in a REDCap database. The ultrasound images from the sonoHSG will be stored in the research PACS.

#### 12. STATISTICAL ANALYSIS

- *Describe how your data will be used to test the hypotheses.*
- State clearly what variables will be tested and what statistical tests will be used.
- *Include sample size calculations.*
- If this is a pilot study, state which variables will be examined for hypothesis generation in later studies.

Standard methods for descriptive statistics will be used, such as means, medians, proportions, and their associated 95% confidence intervals.

Concordance of the results between sonoHSG and HSG will be calculated using Gwet's Agreement Coefficient (AC1). An AC1 of  $\geq$ = 0.80 will be considered successful concordance between the two measures.

A repeated measures analysis of variance (RM-ANOVA) model will be used to examine the effect of treatment (sonoHSG vs. HSG) on the pain measure. The model will include the order in which the treatments are performed and the interaction between order and treatment. If the interaction is not found to be significant, only the main effects of treatment and order will be analyzed.

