#### 16. WITHDRAWAL OF SUBJECTS

- Describe anticipated circumstances under which subjects will be withdrawn from the research without their consent
- Describe procedures for orderly termination

• Describe procedures that will be followed when subjects withdraw from the research, including partial withdrawal from procedures with continued data collection.

The study can be discontinued by the study investigators at any time. Such discontinuation will have no effect on standard patient care.

Subjects can withdraw from the study at any time.

Subjects may be excluded from study analyses due to missing data for one or more of the following reasons:

- Failure to complete both study procedures in the specified time period.
- Failure to complete the pain scale survey.

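### The pain analysis drops the period effect when it is non-significant and keeps a term that does not adjust the sonoHSG–HSG comparison

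*Protocol*

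**What the plan says.** Section 11 of the protocol (Research Procedures) says that "subjects will have both the HSG and SonoHSG performed consecutively", and the Schedule of Events in that section lists "HSG and sonoHSG (order decided via randomization". Pain is scored once per procedure: "The pain scale will be administered verbally immediately after each procedure". In section 10, pain under sonoHSG versus HSG is the only secondary endpoint.

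Section 12 analyses pain by repeated measures ANOVA with a treatment effect. On the other terms it says: "The model will include the order in which the treatments are performed and the interaction between order and treatment". It then reduces the model: "If the interaction is not found to be significant, only the main effects of treatment and order will be analyzed". It names no separate period term and does not define order further.

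Two other passages affect how many subjects are analysed in each order. The Randomization Scheme says "The randomization tables will be set up by the biostatistics department" but not how the orders are balanced. Section 16 says "Subjects may be excluded from study analyses due to missing data for one or more of the following reasons", and the reasons include failure to complete both procedures and "Failure to complete the pain scale survey".

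**The concern.** In the Schedule of Events, order is what randomisation decides for each subject, so the natural reading in section 12 is the sequence (HSG first or sonoHSG first). In a two-period crossover, sequence crossed with treatment is not effect modification. It is the period effect, meaning the change in pain from the first procedure to the second whichever procedure comes first. Such an effect is plausible when two transcervical procedures follow one another.

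The starting model is sound, because its three terms span treatment, period and sequence. The fault lies in the reduction rule, which has two consequences.

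- **Non-significant result.** Period is removed and the sequence main effect stays. The reduced model looks adjusted for order but is an unadjusted paired comparison.
- **Significant result.** The protocol does not say what it means. The usual ANOVA reading of such an interaction is that the treatment effect depends on order, which would misdescribe an ordinary period effect.

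**Working it through.** No figure in the protocol rests on this analysis (30 subjects were chosen for feasibility), so there is none to reproduce. Steps 1 to 3 are exact for complete pairs. Steps 4 to 6 use assumed inputs.

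**1. What the interaction is.** Code sequence +1 for HSG first and −1 for sonoHSG first; treatment +1 for sonoHSG and −1 for HSG; period +1 for second and −1 for first.

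| Cell | Sequence | Treatment | Product | Period |
|---|---|---|---|---|
| HSG first, 1st procedure (HSG) | +1 | −1 | −1 | −1 |
| HSG first, 2nd procedure (sonoHSG) | +1 | +1 | +1 | +1 |
| sonoHSG first, 1st procedure (sonoHSG) | −1 | +1 | −1 | −1 |
| sonoHSG first, 2nd procedure (HSG) | −1 | −1 | +1 | +1 |

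The last two columns agree in every cell, so interaction and period are one contrast. Models fitted to simulated pairs at 15/15 confirm it: interaction −0.48985 and period +0.48985, both with SE 0.20243 (the sign depends only on coding).

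**2. What the retained term does.** In the same data the treatment estimate is −0.57929 (SE 0.43745) with or without the sequence main effect, and equals the mean paired difference. In an 18/12 data set it is −0.57697 with or without sequence, and −0.763 once period is included. Only period adjusts.

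**3. Bias when period is dropped.** Let δ be the treatment effect, π the period effect (second minus first), and n1 and n2 the numbers having HSG first and sonoHSG first. The sonoHSG minus HSG difference has mean δ + π in the first group and δ − π in the second. The overall mean is δ + π(n1 − n2)/(n1 + n2), so the bias is π(n1 − n2)/(n1 + n2). For π = 1 its size is:

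- 15/15: 0
- 12/15: 3/27 = 0.11
- 12/18: 6/30 = 0.20
- 10/20: 10/30 = 0.33

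Its direction depends on which order is over-represented. Keeping period means averaging the two group means, which gives δ for any split.

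**4. The rule as a whole.** Period is sometimes retained, so the average bias is smaller than in step 3. The rule was simulated as follows: full model if the interaction has p < 0.05, otherwise treatment and sequence only. Assumptions: within-subject difference SD 2.5 (range 2.0–3.0), π = 1 (range 0.5–1.5), 30 subjects (27 at 12/15), two-sided 0.05 test.

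| Split | Average bias, size (range) | Type I error |
|---|---|---|
| 15/15 | 0 | 0.049 |
| 12/15 | 0.03 | 0.052 |
| 12/18 | 0.055 (0.002–0.08) | 0.056 |
| 10/20 | 0.10 (0.01–0.135) | 0.073 |

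At 10/20, coverage of the 95% CI is 1 − 0.073 = 92.7%, and root mean squared error is 0.525 against 0.484 with period always kept. At 15/15, power for a 1-point difference is 0.558 under the rule and 0.564 with period kept. With 50 subjects split 20/30, bias is 0.023 and type I error 0.057.

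**5. How often the test is significant with no effect modification.** It compares the two group means of step 3, whose expected difference is 2π, with SE = SD × √(1/n1 + 1/n2). At 15/15 this is 2 / (2.5 × 0.365) = 2.19, giving 56% (14% to 98% over the range). A uniform difference of δ = 1 with π = 1 would then appear as 1 − 1 = 0 points in one order and 1 + 1 = 2 in the other.

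**6. If order means position (first or second).** Order is then period and is always kept, and the interaction becomes the sequence or carryover contrast. For a 1-point carryover, assumed score SD 2.5 and 15 per sequence, its power is 0.101, 0.094 and 0.089 at within-subject correlations of 0.3, 0.5 and 0.7. Dropping it does not change the treatment difference.

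**The case against.** The strongest reply is that the fault needs two readings: order as sequence, and reduction as a refit. Section 12 does not define order, and if it means position the reduced model already contains period. Analysing only main effects could also mean reporting them from the unreduced model, in which case period is never lost.

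The harm is also small. Nothing in the protocol points to a 10/20 split, and under unrestricted 1:1 allocation of 30 subjects a split at least that uneven has a probability of about 10%. Averaged over such allocation, bias is 0, because imbalance falls either way; type I error is 0.051 to 0.056, and power is within about 0.01 of always keeping period. Pain is a secondary endpoint without a success threshold in an unpowered pilot. The allocation method and the reading of a significant interaction may be set out in a statistical analysis plan.

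Much of this stands on size: the biases in the table are conditional on a given imbalance, and misreporting is a risk, not something the protocol announces. It does not rescue the rule. The Schedule of Events uses order for what is randomised. Making the analysis conditional on the interaction test is more naturally read as refitting without that term. The objection is to a rule the protocol states, not to detail it leaves out, and a statistical analysis plan that followed the rule would inherit the fault.

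**Conclusion.** The concern holds and should be corrected. With order as the randomised sequence, section 12 pre-tests the period effect, discards it when non-significant, and keeps a term that adjusts nothing. That part is exact for complete pairs.

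The effect on the estimate is none with equal orders and small otherwise, reaching about 0.1 point on average and a type I error of 0.073 at 10/20 under the central assumptions. Equal orders in the analysed set are not assured. The interpretive risk is larger and exists even at perfect balance, although its 56% depends on the assumed period effect and SD. Under the position reading the treatment difference is unaffected, and the pre-test is merely a carryover test with very low power.

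**What to change.** Replace the reduction rule in section 12 with one statement: the pain model contains treatment, period (first or second procedure) and sequence, with subject as the repeated factor, and the period-adjusted treatment difference is reported with its 95% CI whatever the period p-value. Delete the interaction pre-test. This also settles what order means.

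The repeated measures ANOVA can stay. A comparison of first procedures only could be added as a sensitivity check, since this model cannot remove carryover bias.

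The cost is one sentence of wording and, relative to the reduced model, one residual degree of freedom (28 instead of 29 with 30 complete pairs). No new data are needed, because the order is assigned in REDCap and pain is already scored after each procedure.
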